5.3. Demographic and Baseline Disease Characteristics

All demographics and baseline disease characteristics will be summarized for the FAS population.

Demographic data, including age (years), age category (18-<35, 35-<50, 50-<65, 65-<80, ≥80), gender, ethnicity, race, height, weight, and BMI will be summarized by treatment group and overall.

Baseline ALS disease characteristics will also be summarized. The site of onset, form of ALS, mutant genes among participants with familial ALS (as reported by the PI on the eCRF), current usage status of riluzole and edaravone (Yes or No) and their usage duration (< 30 or ≥ 30 days for riluzole and < 60 or ≥ 60 days for edaravone) and [REDACTED] pre-

CONFIDENTIAL

The information contained herein may not be used, disclosed, or published without the written consent of Biogen MA Inc.

screening slope will be summarized as continuous variables. The duration of ALS symptom onset, duration of ALS diagnosis prior to first dosing, baseline [REDACTED], baseline percent predicted [REDACTED], and baseline plasma NfL and [REDACTED] will be summarized as numeric variables with mean, standard deviation (SD), median, first and third quartiles and the range summarized. Geometric mean and geometric CV% will also be summarized for baseline plasma NfL and baseline [REDACTED]

[REDACTED]

Genetic data from MNG lab central testing and Biogen internal genetic testing will be integrated and summarized for the FAS population. If the FAS population is different to safety population or clinical function population, summaries will also be presented for these populations. [REDACTED]

[REDACTED], SOD1 (presence of pathogenic/likely pathogenic variant Yes or No), FUS (presence of pathogenic/likely pathogenic variant Yes or No), TDP43 (presence of pathogenic/likely pathogenic variant Yes or No), C9orf72 (harbor a pathogenic C9orf72 expansion in at least one allele Yes or No), and UNC13A (number of risk alleles on rs12973192 and rs12608932: 0, 1, or 2).

Additionally, listing of ALS history will be presented along with baseline NfL value, baseline [REDACTED]

[REDACTED]

Medical history will be classified using MedDRA version 26.1 or later if available. A summary of medical history by system organ class and preferred term will also be provided for the safety population.

5.4. Protocol Deviations

Protocol deviations identified during site monitoring will be captured in a protocol deviation log. All protocol deviations will be listed and a summary of major protocol deviations by dose group will also be provided. A listing of participants with protocol deviations due to COVID-19 will be provided if any.

5.5. Study Treatment Exposure and Concomitant Medications

Extent of exposure to study treatment will be summarized for the FAS population, by treatment group and overall. If FAS population is different to safety population, summaries will also be presented for safety population.

Number of participants who received BIIB105 or placebo will be summarized by dose group, as well total cumulative dose in mg.

Study drug compliance percentage up to the last dose of study drug received in Part 1 will be defined as the number of doses actually received divided by the number of doses that the subject is expected to receive during the Part 1 study period and will be summarized descriptively and categorically (<80%, 80%-90%, 90%-100%). For participants who withdrew from Part 1 early, the number of expected doses is the planned number of doses before the time of withdrawal.

CONFIDENTIAL

The information contained herein may not be used, disclosed, or published without the written consent of Biogen MA Inc.

Separate listings will be provided showing what participants were randomized to as well as study drug administration which will include lot numbers.

Duration of exposure and time on study will be summarized descriptively by dose group. Duration of exposure will be calculated as (last dose date – first dose date +1) in days and time on study will be calculated as (end of study date – first dose date +1) in days.

Concomitant medications will be coded using the World Health Organization (WHO) dictionary WHODRUG (Sep 2023) and concomitant non-drug treatments/procedures using the Medical Dictionary for Regulatory Activities (MedDRA) version 26.1 or later if available.

Medications and non-drug treatments are considered concomitant if they are taken during the study. This includes medications/treatment/procedures that were started prior to the date and time of first dose of study drug if their use continued on or after the date and time of first dosing. If the start date is available but start time is missing and the medication/non-drug treatment start date is the same as the first dose date, the medication/non-drug treatment will be considered concomitant. Similarly, if the stop date is available but stop time is missing and the medication/non-drug treatment stop date is the same as the first dose date, the medication/non-drug treatment will also be considered concomitant. Medications/therapies with missing start or stop dates and times, will also be considered as concomitant in the following situations:

- If both the start and stop dates and times of a medication/treatment/procedure are missing.
- If the start date and time of a medication/treatment/procedure is missing and the stop date and time of the medication/therapy occurred on or after the date and time of first dose of study drug.
- If the start date and time of a medication/treatment/procedure therapy occurred prior to the date and time of first dose of study drug and the stop date and time of the medication/treatment/procedure is missing and the medication/treatment/procedure is listed as ongoing.

[figure not shown]
[figure not shown]
If the start date and time of a medication/treatment/procedure occurred prior to the date and time of first dose of study drug and the stop date and time of the medication/treatment/procedure is missing and the medication/therapy is not listed as ongoing, then the medication/treatment/procedure will be considered as concomitant.

The number and percentage of participants taking any concomitant medications will be summarized for the safety population. The number and percentage of participants taking any concomitant non-drug treatments will also be summarized for the safety population.

CONFIDENTIAL

The information contained herein may not be used, disclosed, or published without the written consent of
Biogen MA Inc.

[figure not shown]
CONFIDENTIAL

The information contained herein may not be used, disclosed, or published without the written consent of
Biogen MA Inc.

CONFIDENTIAL

The information contained herein may not be used, disclosed, or published without the written consent of
Biogen MA Inc.

For each of the 100 imputed datasets, change from baseline will be calculated using the imputed datasets, and the change from baseline endpoint will be compared between treatment groups (BIIB105 60 mg vs Pooled Placebo 1+2 and BIIB105 120 mg vs Pooled Placebo 1+2) using an ANCOVA model for continuous endpoints (████████ and pharmacodynamic endpoints). The ANCOVA model will include covariates for each of the corresponding baseline value for the endpoint, baseline plasma NfL, ██████████

████████ The model will be used to present overall LS means and standard errors for each treatment group (Pooled Placebo 1+2, BIIB105 60 mg and BIIB105 120 mg), and LS mean differences for treatment (BIIB105 60 mg vs Pooled Placebo 1+2 and BIIB105 120 mg vs Pooled Placebo 1+2) with corresponding 95% CI and p-values. A combined estimate of the LS means, LS mean differences and standard errors of the 100 imputed datasets will be obtained, where standard errors will be used to obtain 95% CI from PROC MIANALYZE [Little et al, 2002]. Separate ANCOVA models will be used to obtain estimates, 95% confidence intervals and p-values for other visits. ██████████

For analyses of Part 1, ANCOVA model will be performed to compare BIIB105 60 mg vs. Pooled Placebo 1+2 and BIIB105 120mg vs. Pooled Placebo 1+2.

As scheduled visits are different between cohorts A, B, C1, C2 and cohorts D1, D2, scheduled visits from cohorts A, B, C1, C2 might be combined with selected scheduled visits from cohorts D1, D2 when placebo participants from different cohorts are pooled to perform descriptive analysis, multiple imputation and ANCOVA.

CONFIDENTIAL

The information contained herein may not be used, disclosed, or published without the written consent of
Biogen MA Inc.

Table 12 Scheduled Visits from Different Cohorts – Part 1

Endpoints	Scheduled Visits Cohort A, B, C1, C2	Scheduled Visits Cohort D1, D2	Visits Combination
PD biomarkers	Baseline, 29, 57, 85, 130, 175	Baseline, 29, 57, 85, 113, 141, 169	Day 130/141, Day 169/175

CONFIDENTIAL

The information contained herein may not be used, disclosed, or published without the written consent of
Biogen MA Inc.

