5.3. Dosing

5.3.1. Dose Escalation (Part 1)

For each dose escalation, safety (AEs/SAEs, vital signs, ECGs, and laboratory parameters) and available PK data will be reviewed. The proposed dose escalation is illustrated in Figure 1 and the proposed dosing groups are as follows:

Participants with ALS:

Cohort A: BIIB105 5 mg (6 participants) or placebo (2 participants)

Cohort B: BIIB105 20 mg (6 participants) or placebo (2 participants)

Cohort C1: BIIB105 60 mg (9 participants) or placebo (3 participants)

Cohort D1: BIIB105 120 mg (approximately 36 participants) or placebo (approximately 12 participants)

Participants with polyQ-ALS:

Cohort C2: BIIB105 60 mg (3 participants) or placebo (1 participant)

Cohort D2: BIIB105 120 mg (approximately 12 participants) or placebo (approximately 6 participants)

See Section 3.1.2 for details regarding the rationale for the starting dose and dose escalation.

After a cohort (Cohorts A, B, C1, and C2) is fully randomized and at least 36 days have elapsed since the randomization and dosing of the eighth participant, a Sponsor SST will hold a dose escalation meeting to review all available blinded safety data from all randomized participants. There must be a minimum of 6 evaluable participants for the dose escalation meeting to occur. In Cohort C2, all 4 participants must be evaluable for the dose escalation meeting to occur. Evaluable participants are defined as those who have completed 3 dosing visits and the Day 36 CV. This CV occurs 1 week after the Day 29 dose, the dose that is projected to result in the targeted steady-state exposures for the cohort. Dosing of Cohort D1 is dependent on the SST approving the safety of Cohort C1, and dosing of Cohort D2 is dependent on an SST approving the safety of Cohort C2.

For Cohort D1, the safety review will occur after the cohort is fully randomized, and at least 92 days have elapsed since the randomization and dosing of the 36th participant. The SST will review all available blinded safety data from all randomized participants in the cohort, which must include a minimum of 33 evaluable participants (those who completed all of the first 5 dosing visits as well as the Day 92 clinic visit). This review will be for a final safety review for Cohort D1. Should Part 1 be terminated early (per Section 5.2.1 and Section 13.4) prior to reaching randomization of the entire D1 cohort or minimal evaluable criteria as defined, a final

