13.3.4. Clinical Function and Quality of Life Measures

The actual scores and changes from baseline in each measure will be summarized using descriptive statistics. Missing data will be imputed using multiple imputation. Multiple imputation will be performed on actual values, domains, total scores, or summary scores depending on the endpoint. In addition, each clinical function measure will be analyzed using an ANCOVA model. The model may include covariates such as corresponding baseline value, baseline NfL, duration from onset of symptoms to the first dose of study treatment, and riluzole or edaravone use. The model will be used to estimate least-square (LS) means for each treatment group with standard errors (SEs), and LS mean differences between treatment groups with corresponding 95% confidence intervals (CIs). The p-values comparing treatment differences will also be presented.

For integrated analyses of Part 1 and Part 2 for Cohorts D1 and D2, treatment groups will be defined as Early-start BIIB105 (i.e., those who initiated BIIB105 in Part 1) and Placebo/Delayed-start BIIB105 (i.e., those who received placebo in Part 1), with baseline defined as Part 1 baseline. Clinical function data will be presented by the 120 mg dose level and treatment group (Cohort D1+D2 Early-start vs Placebo/Delayed-start). They will also be presented by cohort and treatment group as a sensitivity analysis (Cohort D1 Early-start vs Placebo/Delayed-start; Cohort D2 Early-start vs Placebo/Delayed-start).

[figure not shown]

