The information contained herein may not be used, disclosed, or published without the written consent of Biogen MA Inc.

Table 13: Seed used for each PD endpoint in MI

Endpoint	Seed
Plasma NfL	3847243

Statistical Analyses

For the statistical analysis of PD biomarkers, the data will be transformed using the natural logarithmic scale.

The following statistical analyses will be evaluated in PD population:

For analyses of Part 1, ANCOVA model will be performed for BIIB105 60 mg vs. Pooled Placebo 1+2 and BIIB105 120 mg vs. Pooled Placebo 1+2.

An ANCOVA model for log ratio to baseline will be performed on change from baseline values on log scale (i.e. $\log(\text{postbaseline}) - \log(\text{baseline})$) for each of the 100 imputed datasets for each PD biomarker. The model will include covariates for the corresponding baseline value, i.e. log value, baseline disease duration since symptom onset, and use of riluzole or edaravone. The least square (LS), i.e. adjusted mean of each treatment group, as well as the treatment group differences will be presented with 95% confidence intervals (CIs) and the p-value.

The following plots over time will be presented for each PD biomarker using the MI imputed datasets where appropriate:

- Arithmetic mean ratio to baseline with standard error bars
- Geometric mean ratio to baseline with standard error bars

Listing of individual data will also be provided.

CONFIDENTIAL

The information contained herein may not be used, disclosed, or published without the written consent of Biogen MA Inc.

CONFIDENTIAL

CONFIDENTIAL

CONFIDENTIAL

CONFIDENTIAL

6. Changes from Protocol-Specified Analyses

- As we do not expect to see many events during the 6 month period, we remove the time to event analyses since symptom onset.

7. References

Protocol 275AS101 Protocol Version 5.0

275AS101 Unblinding Plan Version x.0

CONFIDENTIAL

The information contained herein may not be used, disclosed, or published without the written consent of
Biogen MA Inc.

[REDACTED]

[REDACTED]

[REDACTED]

CONFIDENTIAL

The information contained herein may not be used, disclosed, or published without the written consent of
Biogen MA Inc.

APPENDICES

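### The SAPs do not say that the ANCOVA residual degrees of freedom are supplied to PROC MIANALYZE; on the procedure's default the imputed 95% CIs would be slightly too narrow, and materially so only in a D2-only model

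*SAP*

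**What the plan says.** The Part 1 SAP describes its imputed ANCOVA between Sections 5.5 and 5.6.2. The heading there is not legible; the text corresponds to Section 5.6.1 of the final SAP. It first pools over the imputations: "A combined estimate of the LS means, LS mean differences and standard errors of the 100 imputed datasets will be obtained". It then says how the intervals are formed: "where standard errors will be used to obtain 95% CI from PROC MIANALYZE". Final SAP Section 5.6.1 uses the same wording.

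The contrasts named in the Part 1 text are pooled ones: "ANCOVA model will be performed to compare BIIB105 60 mg vs. Pooled Placebo 1+2 and BIIB105 120mg vs. Pooled Placebo 1+2". For the biomarkers, Part 1 SAP Section 5.9 gives the model terms: "The model will include covariates for the corresponding baseline value, i.e. log value, baseline disease duration since symptom onset, and use of riluzole or edaravone". In the final SAP the imputed ANCOVAs for ALSFRS-R, HHD and SVC (Sections 5.6.2 to 5.6.4 and Table 3) are specified for Cohorts D1 and D2 combined, early start against placebo/delayed start.

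A comparison within Cohort D2 appears in Protocol Section 13.3.4, for the integrated clinical function data: "They will also be presented by cohort and treatment group as a sensitivity analysis". Final SAP Section 5.6.1 makes that presentation optional.

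The final SAP also gives the small sample as a reason for using many imputations, and plans a relative-efficiency check with a threshold near 98%. The legible text of neither SAP mentions complete-data degrees of freedom or a small-sample adjustment.

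**The concern.** Rubin's combining rule has a large-sample form, in which the degrees of freedom depend only on the number of imputations and the fraction of missing information. It also has a small-sample form (Barnard-Rubin), which caps them by what the completed-data model contains. As a matter of general software knowledge, PROC MIANALYZE uses the first unless the residual degrees of freedom are supplied. With 100 imputations the first form gives hundreds or thousands of degrees of freedom whether the model was fitted to 86 participants or to 18.

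The result would be odd: an ANCOVA with no missing data uses its own residual degrees of freedom, so imputing missing values would lead to a more confident reference distribution than having complete data. Intervals would be too narrow and p-values too small. Raising the number of imputations does not help, because it moves the default further towards the normal quantile.

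**Working it through.** The documents state no degrees of freedom, interval width or coverage, and the power inputs are redacted, so there is no figure of the plan's own to reproduce. The check is of size only.

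**Inputs**
- Imputations: m = 100 (both SAPs).
- Planned group sizes (Protocol Section 5.3.1): 60 mg, 9 + 3 = 12; 120 mg, 36 + 12 = 48; placebo, 2 + 2 + 3 + 12 + 1 + 6 = 26. The Part 1 three-group model has 12 + 48 + 26 = 86. Integrated D1+D2 has 48 + 18 = 66. Cohort D2 alone has 12 + 6 = 18.
- Model parameters: intercept, treatment terms, and four covariates (endpoint baseline, baseline NfL, disease duration, riluzole/edaravone as one indicator). This gives 7 with three groups and 6 with two. Residual degrees of freedom v are therefore 86 − 7 = 79, 66 − 6 = 60 and 18 − 6 = 12. Using 6 or 8 parameters in the Part 1 model changes the widening by less than 0.1 percentage point.
- Fraction of missing information λ: not given. Assumed 10 to 40%.

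**Default degrees of freedom:** ν_m = (m − 1)/λ². At λ = 0.1, 0.2, 0.3 and 0.4 this is 99/0.01 = 9,900; 99/0.04 = 2,475; 99/0.09 = 1,100; 99/0.16 = 619. The 97.5% quantile is 1.960 to 1.964 in every model.

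**Barnard-Rubin degrees of freedom:** ν_obs = [(v + 1)/(v + 3)] × v × (1 − λ), and ν = 1/(1/ν_m + 1/ν_obs).

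Part 1 model, λ = 0.2: ν_obs = (80/82) × 79 × 0.8 = 61.7, so ν = 60.2. The quantile is 2.000 against 1.961, which is 2.0% wider. The chance that |t| on 60.2 df exceeds 1.961 is 5.45%.

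D2 alone, λ = 0.3: ν_obs = (13/15) × 12 × 0.7 = 7.28, so ν = 7.2. The quantile is 2.349 against 1.962, which is 19.7% wider. The true level is 8.9%.

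**Results over λ = 10 to 40%**

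| Model | N | v | ν, Barnard-Rubin | Correct CI wider by | True level of nominal 5% test |
|---|---|---|---|---|---|
| Part 1, three groups | 86 | 79 | 68.9 to 43.0 | 1.8–2.7% | 5.4–5.6% |
| Integrated D1+D2 | 66 | 60 | 52.0 to 33.0 | 2.4–3.6% | 5.5–5.8% |
| D2 alone, if fitted | 18 | 12 | 9.4 to 6.2 | 15–24% | 8.0–9.6% |

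If the 60 mg contrast were instead fitted on its own with placebo (12 + 26 = 38, v = 32), the default interval would be 4.0 to 8.0% too narrow over λ from 0 to 0.5.

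**Simulation check** (complete data, 40,000 ANCOVAs per case): with the 1.96 quantile, coverage was 94.5% for the pooled model (v = 79) and 92.7% for 12 vs 6 (v = 12). With the t quantile it was 94.9% and 95.1%.

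**Would the planned relative-efficiency check catch this?** No. Relative efficiency is 1/(1 + λ/m): 0.999 at λ = 0.1 and 0.995 at λ = 0.5, above the 98% mark. It shows whether there are enough imputations and says nothing about residual degrees of freedom.

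**The case against.** A reader might infer that the SAPs leave the residual degrees of freedom out, so that every imputed interval is certainly too narrow. The documents do not support that. They name the procedure but not its options, and programming specifications outside these documents may supply the value. Redacted text also adjoins the Part 1 paragraph. The silence is better established in the final SAP, where the parallel paragraph is legible and has no such provision. This part of the objection stands: the narrowing is conditional on the default being used.

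A reader might also infer that the protocol requires an imputed ANCOVA in the polyQ cohort alone, so that the D2 figures describe a planned analysis. Protocol Section 13.3.4 says that by-cohort data will be presented as a sensitivity analysis; it does not say that a separate imputed model will be fitted to 18 participants. The final SAP makes the by-cohort presentation optional. The Part 1 contrasts pool polyQ and non-polyQ participants, and genetic subgroup analyses in Part 1 (Part 1 SAP Section 3.3) are optional. This also stands.

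Finally, no decision is shown to turn on the point. The primary endpoint is the incidence of adverse events and serious adverse events. The error would favour false positives, whereas the final SAP (Section 1) reports that the study stopped because no neurofilament effect or clinical benefit was seen.

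What the objection does not remove is that both SAPs fix the seeds, sort order, variable coding and number of imputations, yet leave open the setting that determines the reference distribution.

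**Conclusion.** The point holds as a specification gap of minor size. On the default, the specified contrasts lose about 2 to 4% of interval width, and a nominal 5% test runs at 5.4 to 5.8%. The gap becomes material only if a D2-only imputed ANCOVA is run. For NfL and ATXN2 only Part 1 is affected, because final SAP Section 5.9 plans no further pharmacodynamic or biomarker analyses. Clinical function contrasts are affected in the integrated analysis as well.

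The sizes rest on the software default, an assumed 10 to 40% of missing information, the planned cohort sizes, and 6 or 7 model parameters. The direction rests only on the default being used.

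**What to change.** In the imputation and ANCOVA text and Section 5.9 of the Part 1 SAP, and in Section 5.6.1 of the final SAP, state that the residual degrees of freedom of each ANCOVA are supplied to PROC MIANALYZE through EDF=, so that all 95% CIs and p-values use Barnard-Rubin small-sample degrees of freedom. The value must be set for each model, including any by-cohort model that is run.

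The cost is one clause and one program option. Point estimates and standard errors do not change; intervals become slightly wider. If the programs already do this, the clause documents it.

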5.6.2. ALSFRS-R

General Description

The ALSFRS-R is a questionnaire to measure degree of impairment in 4 functional domains: respiratory function, bulbar function, gross motor skills, and fine motor skills. Each domain consists of 3 items, each scored from 0 to 4, with higher scores representing better function. Each domain can have maximum score of 12 and the total possible score for ALSFRS-R is 48. The items for each domain are listed below.

- Respiratory function: dyspnea, orthopnea and respiratory insufficiency
- Bulbar function: speech, salivation and swallowing
- Gross motor skills: turning in bed, walking and climbing Stairs
- Fine motor skills: handwriting, cut and handling utensils without or with gastrostomy, dressing and hygiene

CONFIDENTIAL

The information contained herein may not be used, disclosed, or published without the written consent of
Biogen MA Inc.

[figure not shown]

